
Secondary objective(s):
	
 
1. To explore the association between the trans-impedance and intra-cochlear voltage measurements, NRT thresholds and the intra-cochlear electrode array position.
 
2. To investigate changes in the trans-impedance and intra-cochlear voltages along with NRT thresholds over time to identify the stability of the measurements.
 
3. To establish a database of trans-impedance and intra-cochlear voltages, NRT thresholds and CT/DVT images for educational, research and development purposes.
 
				

Treatment and follow up schedule:
	
Procedure
	
Pre-op
	
Surgery
	
First Activation
	
3 months post-op

	
Informed Consent
	
X
			
	
Demographics, Medical & Hearing History
	
X
			
	
Surgical questionnaire
		
X
		
	
Voltage tomography and impedance matrix
		
X (after electrode insertion)
	
X
	
X

	
Auto NRT thresholds
		
X (after electrode insertion)
	
X
	
X

	
CT/DVT Scan
	
X
	
X (after electrode insertion, may be done after surgery)
		
	
(S)AE, ADE, DD
		
X
	
X
	
X

	
Protocol deviations
		
X
	
X
	
X

Primary endpoint:
	
Trans-impedance and intra-cochlear voltage measurements for each electrode contact after electrode insertion with post-operative CT/DVT Scan.
				

Secondary endpoints:
	
 
1. NRT thresholds for each electrode contact during surgery and pre-operative CT/DVT Scan co-registered with the post-operative CT/DVT Scan collected for the primary endpoint.
 
2. Trans-impedance and intra-cochlear voltage measurements and NRT thresholds for each electrode contact at first activation and 3 months post-operative
 
3. Validated database entry of trans-impedance and intra-cochlear voltage measurement and NRT thresholds during surgery, at first activation and three months post-operative as well as the pre-operative and post-operative CT/DVT Scans respectively.
 
				

## 2 Terms and Abbreviations

Term	Definition
Trans-impedance measurement	An impedance measurement is a calculated measurement obtained by dividing the voltage difference between two electrodes by the current applied to obtain this voltage. A trans-impedance measurement is similar to an impedance measurement except that the current applied to obtain the voltage is not applied to electrodes from which the voltage measurement is obtained.
Specificity	The true negative rate . The measure of the proportion of negatives that are correctly identified as such (i.e., the percentage of normal insertions, as verified by CT/DVT scan, that are correctly identified via an algorithm as not having an anomalous position).

Abbreviation	Definition
TIM	Trans-impedance matrix
CSEP	Custom Sound™ Electro Physiology
EC	Ethics Committee
NRT	Neural Response Telemetry
PIC	Patient Informed Consent form
DICOM	Digital Imaging and Communications in Medicine
CRF	Case Report Form
eCRF	Electronic Case Report Form
AE	Adverse Event
CPM	Clinical Project Manager
GCP	Good Clinical Practice
DD	Device Deficiencies

## 3 Introduction

At the beginning of 2017 the global number of cochlear implant (CI) recipients have reached approximately 400'000. CIs are indicated for ears with moderately severe to profound hearing loss as referenced in the current labelling. It is anticipated that this number will significantly increase over the coming years because of the ageing of the population globally and an increase in awareness regarding the restorative hearing benefits a CI can bring. Given these expectations on future CI demands CI manufacturers need to focus their developments on the expectations of health care systems as well as patients' needs and requirements of professionals.

Severe to profound deafness is typically caused by a degeneration of the inner hair cells (IHCs) in the inner ear are responsible for the initiation of neural spikes. In their absence, the information to the auditory cortex is affected. A CI bridges the IHCs by direct electrical stimulation of the peripheral auditory nerve. For optimal patient outcomes, it is important that

the CI electrode (see figure 1) is surgically placed in the inner ear (in scala tympani), close to the excitable tissue.

[figure not shown]

Figure 1: Optimal position of perimodiolar electrode array

For various reasons, the intra-cochlear position of the electrode may be suboptimal. The insertion angle may be too shallow or too deep; the electrode may buckle; a perimodiolar array may take a lateral trajectory away from the nerve; or the tip may fold over. Ramos et al. (in press, 2016) has addressed risk mitigation of sub-optimal intra-cochlear electrode placement after insertion. These modalities occur at a low incidence rate (a few percent, Dirr et al. 2013, Grolman et al. 2008, Zuniga et al. 2016), but may be associated with degraded hearing outcomes (Zeh & Baumann HNO 2015 63 (8):557-576.) It is therefore desirable to be able to detect these anomalies in the operating theatre so that the surgeon has the opportunity to correct them.

The gold standard to verify the electrode position currently is through radiological imaging techniques, such as CT scan or X-ray. This imaging increases the cost and duration of the procedure and often includes radiation which may put the patient at risk of 'radiation-related' disease according to the Recommendations of the International Commission on Radiological Protection. In other instances, the logistical burden of obtaining intra-operative imaging leads to the electrode array placement being verified post-operatively, meaning either the electrode position is left uncorrected or an additional surgery is required.

An alternative to medical imaging may be objective measures. State of the art implant systems can not only stimulate but also contain a measurement amplifier, e.g. to capture the auditory nerve's response to electrical stimulation, known as electrically evoked compound action potential (eCAP). The amplifier is also capable of measuring the voltage on an arbitrary electrode pair; this capability is routinely used to obtain impedance measurements during surgery by measuring the voltage on the stimulating electrode pair and dividing this voltage by the current applied ( $R=V/I$ ). In addition to this routine measure, the amplifier can also be configured to measure the intra-cochlear voltage field -resulting from the stimulation of one electrode pair- along the entire electrode array; i.e. the electrical spread curve. This technique is known as electrical voltage telemetry (EVT) or electrical field imaging (EFI). The full set of electrical spread curves, normalised by the current is known as the trans-impedance matrix (TIM). An example is shown in figure 2.

---

 Since the stimulation and recording electrode are not necessarily identical, this value is called a trans-impedance instead of an impedance

[figure not shown]

Figure 2: Trans-impedance measure for electrode 11

Literature (Vanpoucke, 2004) reports that there is significant variability in these curves, due to the variation in anatomy, electrode position and tissue reaction. However, it has been observed that the information contained in a trans-impedance matrix can be correlated to some aspects of the electrode array position (Vanpoucke et al. 2012, Zuniga et al. 2016) and algorithms are being developed that use trans-impedance and intra-cochlear voltage measurements to provide feedback on the electrode array position. One such algorithm, developed by Ramos et al. uses this information to detect whether the electrode tip has folded over or whether the electrode array is potentially outside the cochlea. However, given the variability between ears, the tuning of the threshold parameter in this algorithm (is the implantation normal or not?) needs to be explored to determine the sensitivity and the specificity.

The long-term aim is for this and other proposed algorithms, when implemented in a device that communicates with the cochlear implant, to provide feedback on the electrode array position immediately after or during insertion of the electrode. If sufficiently sensitive, the feedback provided by such algorithms can help surgeons make informed decisions on the appropriate course of action, which may include obtaining imaging to confirm the position of the electrode array and subsequent repositioning before closure of the surgical procedure, to achieve optimal outcomes. This will reduce the need for post-operative radiological diagnostics and avoid unnecessary re-operations to correct inappropriate placement of the electrode array. In addition, if it can be demonstrated that an algorithm has sufficient diagnostic specificity (the ability to correctly diagnose successful electrode insertions), its feedback might replace the need for routine intra-operative radiological imaging to confirm good electrode placement.

This clinical investigation will gather trans-impedance and intra-cochlear voltage measurements intra- and post-operatively. These measurements can be used to characterise the electrical properties of the electrode array and the surrounding tissue in the cochlea after insertion. This data will be used to explore the specificity of the [name] candidate algorithm. Given the low incidence of anomalous electrode position cases in normal clinical practice (Dirr et al. 2013) and the inability to deliberately generate anomalous electrode positions in patients; this study is only focussed on exploring the specificity. (negative results divided by true negative cases) of the algorithm. An exploration of the sensitivity (positive results divided by true positive cases) of the candidate algorithm is out of scope for this study. A separate in vitro study where anomalous insertions can be purposely created will be conducted to explore the sensitivity.

 For statistical purposes, it is assumed that this study will show the algorithm able to achieve  $\geq 98\%$  specificity with a 90% confidence.

For the purpose of quantifying the accuracy of a diagnostic algorithm, the following terminology is used:

- Positive case – a case in which electrode insertion results in an anomalous position.
- Negative case – a case in which electrode insertion is successful and position is not anomalous.
- True positive response – The candidate algorithm correctly detects the presence of an anomalous electrode position.
- False positive response – The candidate algorithm incorrectly indicates an anomalous electrode position when none is present.
- True negative response – The candidate algorithm correctly indicates no anomalous electrode position when none is present.
- False negative response – The candidate algorithm fails to detect an anomalous electrode position even though one is present.
- Sensitivity - the number of true positive responses divided by the number of positive cases (anomalous positions).
- Specificity - the number of true negative responses divided by the number of negative (non-anomalous) cases.
- Positive predictive value – the probability that given a positive response the electrode position is anomalous
- Negative predictive value – the probability that given a negative response the electrode position is not anomalous

The candidate algorithm is provided with the trans-impedance measurements and indicates whether a tip fold-over or array outside the cochlea have been detected. For the feedback from this algorithm to be clinically useful it must be shown that the specificity is sufficiently high to ensure that the surgeon is not unnecessarily prompted to take action (confirmation of electrode position by imaging) when not required. Current methods for detecting anomalous electrode position without relying on imaging either use manually-perceived force feedback from the electrode array (Dirr et al. 2013, Pile et al. 2013) or measurement of neural activity, (Grolman et al. 2008, Zuniga et al. 2016). Dirr et al. shows a positive predictive value of 29% using the sense of increased physical resistance during insertion whereas Grolman did not comment on the positive predictive value of the spread of excitation technique and Zuniga stated it was not clear. In the current study the aim is to show that using an algorithm based on the trans-impedance matrix a positive predictive value of twice that observed by Dirr et al. can be achieved, thus the aim is a positive predictive value of 60%.

Following the initial analysis as outlined in this investigation plan, future candidate algorithms developed for the purpose of detecting anomalous electrode position will be evaluated using the data as collected within the current investigation.

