## 5 Justification for the design of the clinical investigation

Several researchers have demonstrated the utility of trans-impedance matrix and other voltage measurements (Hey et al. 2015, Vanpoucke et al. 2004, Vanpoucke et al. 2012) to identify the intra-cochlear electrode positioning. The current investigation is designed to both evaluate a candidate algorithm for detecting the occurrence of gross anomalies in position (e.g. tip fold-over or the electrode array not in the cochlea) and to provide a robust dataset in a clinically representative sample of cochlear implant recipients that can be used to test the specificity and sensitivity of future electrode position feedback algorithms. Such algorithms have potential clinical application in providing objective feedback to the surgeon at the time of electrode insertion to inform the surgeon on electrode placement without additional radiological imaging, and may in future lead to improved clinical outcomes for cochlear implant recipients.

No large database of combined high quality imaging of the intra-cochlear electrode position and reliable trans-impedance measurements exist. It is only relatively recently that it has become possible to determine accurate intra-cochlear electrode position, as a result of advances in scanner technology. Also, the trans-impedance measurements (contained in Custom Sound™ Electro Physiology) that will be used in the study only recently became available. Earlier versions of this tool did not provide sufficient resolution to accurately measure the electrical spread curves.

To explore the decision algorithm, a large dataset is needed. This study will systematically collect a large pool of trans-impedance measurements of CI recipients combined with state of the art imaging of the implanted electrode as part of the clinical routine. Image analysis will allow an expert radiologist/ENT surgeon to determine for each implantation whether it is a normal case or not. The trans-impedance measurements will be analysed by the decision algorithm, and the agreement with the human experts will be established. This exploration of the specificity of the candidate algorithm is the main target of this study, thus being evaluated on the bench without patient involvement.

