### **6.2 Anticipated adverse device effects**

The potential adverse device effects while using the components listed in section 4 to generate electrical stimulation of the cochlea during surgery and during the routine visits after surgery are no greater than that posed through the clinical routine via NRT, facial nerve monitoring, etc. All devices used in this clinical investigation are CE marked and TGA approved.

The study participants will undergo a standard cochlear implantation surgery, and are therefore identical to the risks in cochlear implant surgery as described by the package insert. No feedback on analysis of the intra-operative measurements will be provided to the surgeon during the operation.

The trans-impedance and Auto NRT measurements will be performed with the CSEP software and therefore be subject to the standard adverse events associated with the use of this software. The measurements will be performed by expert clinicians trained on the use of this software in normal clinical practice. The risks of participating in this study are therefore identical to the risks in normal clinical care.

The candidate algorithm is run on the data by an independent party at specified intervals on the data collected by the above-mentioned components. The person who performs the analysis does so in de-identified data after study closure. The algorithm evaluation will be conducted on the bench without any patient involvement. Thus, there are no anticipated adverse events resulting from the use of the algorithm.

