2.1 Overview

A total of 154 patients will be assessed in the statistical analysis of the data. This will serve to collect a representative sample of the variability of surgical techniques across clinics and surgeons. The confidence interval to be used in the analyses will be a 90% two-tailed. This confidence interval was deemed to be satisfactory due to the exploratory nature of the study. The statistical analyses conducted for the primary and secondary objectives will lead to the endpoints of the study.

The statistical analysis will be conducted by [REDACTED], Cochlear).

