2.2 Sample size calculation

The goal of the candidate algorithm is to indicate to surgeons and medical staff whether an electrode tip fold-over or electrode outside cochlea appears to have occurred, which should be confirmed radiographically. A target specificity of 98% and confidence level of 90% have been selected.

The 98% specificity target initialises the calculation of the required sample size (N). Since the specificity of the algorithms can only be estimated from a sample population, there is required to be a reasonable expectation that the specificity estimate is equal to or greater than the specificity target. To ensure that the reasonable expectation is fulfilled, the 98% specificity target is set to be the lower bound of the 90% binomial confidence interval for an estimated or measured specificity of 100%. The selected sample size must fulfil this requirement. The binomial confidence interval will be calculated using the Clopper-Pearson exact method and is denoted by Equation 1 and Equation 2:

$$P_{LB} = p : \sum_{i=0}^x \binom{n}{i} p^i (1-p)^{n-i} \approx \frac{\alpha}{2}, \quad \text{for } 0 \leq p \leq P \quad (1)$$

$$P_{UB} = p : \sum_{i=x}^n \binom{n}{i} p^i (1-p)^{n-i} \approx \frac{\alpha}{2}, \quad \text{for } P \leq p \leq 1 \quad (2)$$

where P_{LB} is the lower bound of the binomial confidence interval, P_{UB} is the upper bound of the binomial confidence interval, P is the measured probability of success, p is the probability of success, n is the number of trials, i is the number of successes, x is the measured number of successes and $\alpha = 0.1$ is the level of significance for the 90% confidence interval.

In the Clopper-Pearson method, n is the unknown input in the equation. To find n requires taking into account that there may be occurrences of electrode anomalies in the sample. The range of the possible numbers of anomalies must be estimated such that there is an expected sufficient number of samples (n) to estimate specificity. The sufficient number of samples is calculated by Equation 3 and Equation 4:

$$n = N - m \quad (3)$$

$$m = i : \sum_{i=0}^N \binom{N}{i} p^i (1-p)^{N-i} \approx 0.90, \quad \text{for } 0 \leq i \leq N \quad (4)$$

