where n is the number of sufficient samples required to estimate specificity, N is the total sample size or number of patients required, i is the number of anomalies and p is the probability of an anomaly. We assume that the most prevalent anomaly condition will be a tip foldover. For p we use an estimate of 0.04139 or 4.14% which is based on the perimodiolar weighted average percentage between Grolman et al. (2009) and Zuniga et al. (2017). m is then approximately an upper bound on the number of expected tip fold-overs based on the 90th percentile of the cumulative binomial distribution. In other words, there is at least an approximate 90% chance that there will be m number of tip fold-overs or less.

Determining the sample size N is an iterative process. N is increased from 0 and for each value of N , n is calculated using Equations 3 and 4 which allows for P_{LB} to be calculated using Equation 1. Once P_{LB} is approximately 0.98 or 98%, the corresponding N is selected as the sample size.

Using the denoted method (see Appendix A) a sample size of $N = 154$ was selected which had a 89% chance of 9 or less tip fold-overs taking place, resulting in an $m = 9$ and $n = 145$. With a measured specificity (i.e. estimated specificity) of 100% and $n = 145$, the $P_{LB} = 0.9797$ which is approximately 98%.

With an algorithm target specificity of at least 98%, a target sensitivity of at least 90%, an estimated probability of a tip fold-over of 4.14%, the positive predictive value (PPV) is equal to 66.02%. This entails that after the algorithm has detected a tip fold-over, it is estimated that two thirds subset of patients will be confirmed by imaging to have a tip fold-over. The calculation of PPV is calculated by Equation 5:

$$PPV = \frac{(prevalence * sensitivity)}{(prevalence * sensitivity) + ((1 - prevalence) \times (1 - specificity))} \quad (5)$$

$$PPV = \frac{(0.0414 * 0.90)}{(0.0414 * 0.90) + ((1 - 0.0414) \times (1 - 0.98))} = 0.6602 \quad (6)$$

where in this application *prevalence* is the estimated rate of tip fold-overs.

3 Conduction of statistical analysis

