3.1 Primary objective

The primary objective of the study is to explore the specificity of an algorithm that detects low incidence anomalies such as tip fold-overs or an electrode migration. The target maximum specificity of the algorithm has been selected to be 98%. The following steps will be run to explore the specificity up to this upper bound:

1. Run the candidate algorithms on each of the patient's data
 - Patients with 'normal' insertions (89% chance of at least 145 patients)
2. Collect the output of the algorithm

- The outputs of the algorithms will be Boolean in nature; 0 represents no tip fold-over or electrode outside the cochlea and 1 represents an tip fold-over or electrode outside the cochlea
3. Count the number of patients that have been classified as not having an anomaly by the algorithm.
 4. Conduct radiographic analysis of each insertion to classify as either normal or abnormal. Document in the latter case the reason for the classification in the anomaly category. .
 5. Calculate the percentage of patients (P) that have been correctly classified as not having an anomaly
 6. Calculate the lower bound of the 90% binomial confidence interval (P_{LB}) for the true success rate (specificity) of the algorithm using Equation 1

If the calculated lower bound of the 90% binomial confidence interval around p is equal to or greater than 98%, the candidate algorithms can be stated to have an expected specificity equivalent to or greater than 98% with 90% confidence. As explained in Section 4, the candidate will have reached the upper limit of specificity of 98% with 90% confidence if 100% of at least 145 normal insertions are correctly classified as normal.

3.2 Secondary objective 1

The first secondary objective of this study is to explore the association or relationships between the trans-impedance, intra-cochlear voltage measurements and NRT thresholds and the intra-cochlear electrode position. This will be conducted by:

1. Measuring the intra-cochlear electrode array position for 22 electrodes for each patient from CT images
2. Univariate and multivariate analysis
 - a. Visualisation (descriptive statistics)
 - b. Feature extraction
 - c. Correlation and ANOVA analysis
 - d. Statistical modelling

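### SAP 3.1 allows the 98% specificity claim for an unstated number of algorithms, and neither document fixes a version or threshold before the study data are used

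*Protocol*

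**What the plan says.** **One algorithm or several.** The hypotheses (Protocol 7, SAP 1.4) and the analysis in Protocol 9.2 are written for one algorithm. Protocol 3 places other algorithms after the initial analysis. SAP 3.1 departs from this. Its first step is "Run the candidate algorithms on each of the patient's data", and its success statement is that, if the lower bound reaches 98%, "the candidate algorithms can be stated to have an expected specificity equivalent to or greater than 98% with 90% confidence". No number of algorithms, list or multiplicity rule is given.

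**Threshold.** Protocol 3 says that "the tuning of the threshold parameter in this algorithm (is the implantation normal or not?) needs to be explored". Protocol 5 says "To explore the decision algorithm, a large dataset is needed" and that this study will collect it. Neither document gives a threshold value, a version, a lock date or a tuning set kept apart from the test set.

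**Timing.** Protocol 6.2 has the algorithm "run on the data by an independent party at specified intervals", while its next sentence places the analysis after the study has closed. Protocol 9.1 and SAP 4 also place the analysis at the end.

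**Sensitivity.** Protocol 3 puts it out of scope and assigns it to a separate in vitro study.

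**The concern.** The pass rule gives its nominal protection when one decision rule, fixed beforehand, meets the data once. The plan states H0 and H1 and allows a claim when the rule is met, but it leaves both the algorithm and the cut-off open. These two freedoms do different harm.

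- **Choosing among different algorithms** gives several chances of a clean score and raises the chance of a false claim.
- **Tuning one cut-off on the evaluation ears** lets the analyst place it just beyond the most extreme normal ear. The rule is then met whatever the quality of the algorithm. The price is paid in missed anomalies, and the evaluation set holds none by design.

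The result matters beyond this study. Protocol 3 links sufficient specificity to replacing routine intra-operative imaging.

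**Working it through.** **Inputs from the documents**
- Interval (SAP 2.1): "The confidence interval to be used in the analyses will be a 90% two-tailed", so 0.05 lies in the lower tail.
- Target (SAP 2.2): "A target specificity of 98% and confidence level of 90% have been selected".
- Anomaly rate: 0.04139; N = 154, m = 9, n = 145; lower bound 97.97% at 145/145 (SAP 2.2, Protocol 9.1).

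**Assumption:** the number of algorithms K is not in the documents, so a range is shown.

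**1. The plan's own figures**
- Rate: 9 / (0.48 × 303 + 72) = 0.04139.
- P(9 or fewer fold-overs in 154) = 89.2%.
- Exact lower bound at 145/145: 0.05^(1/145) = 97.955%. The grid search in SAP Appendix A returns 97.975%, which explains the printed 97.97%.

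The plan treats 145/145 as a pass, and so do the steps below. Read strictly, a bound of at least 98% needs 149 normal insertions.

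**2. One fixed algorithm**

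P(145/145) = s^145 at true specificity s.

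| True specificity | Chance of 145/145 |
|---|---|
| 95% | 0.06% |
| 97% | 1.2% |
| 98% | 5.3% |
| 99% | 23% |

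A fixed rule is a demanding test: poor rules almost never pass. With 149 normal insertions the figure at 98% is 0.98^149 = 4.9%.

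**3. Any one of K different algorithms may carry the claim**

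For independent algorithms, each with true specificity 98%, the chance that at least one passes is 1 − (1 − 0.0534)^K.

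| K (assumed) | Chance of at least one false pass |
|---|---|
| 1 | 5.3% |
| 2 | 10.4% |
| 3 | 15.2% |
| 5 | 24.0% |
| 10 | 42.3% |

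Algorithms run on the same matrices from the same ears would be correlated, which lowers these figures. With full correlation the chance stays at 5.3%.

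**4. One threshold tuned on the same normal ears**

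Take one continuous score and one monotone cut-off, set at the most extreme of 145 independent normal ears. Its true specificity follows a Beta(145, 1) distribution, so P(true specificity < 98%) = 0.98^145 = 5.3%. This equals the fixed-rule figure, because the zero-false-positive events are nested. The observed result, however, is 145/145 with probability 1, against the pass rates in step 2 for a fixed cut-off.

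**5. What lost sensitivity would mean for the plan's own aim**

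SAP Equation 5, with prevalence 0.0414, specificity 0.98 and sensitivity 0.90, gives a positive predictive value of 66.02%, as printed. Keeping specificity at the claimed 98%, the 60% aim of Protocol 3 is reached only if sensitivity is at least (0.6/0.4) × (0.9586 × 0.02) / 0.0414 = 0.69. At a sensitivity of 50% the value is 0.0207 / (0.0207 + 0.01917) = 52%. A higher true specificity would offset part of this. Data from normal ears alone cannot show where the sensitivity lies.

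**The case against.** The strongest reply is that the plan evaluates one identified algorithm. Protocol 3, 9.1 and 9.2 and the hypotheses are singular, other algorithms come later, and no comparison or choice of a best performer is described. A reader might infer from SAP 3.1 that the trial sets out to test several algorithms and pick a winner. The documents do not support that. The plural permits it without planning it, and K and independence are assumptions.

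Three further points stand.
- **Tuning.** Protocol 3 says that tuning needs exploring, but not that these ears will be used for it. A reader might also infer that tuning one threshold inflates the false-claim rate. For a single monotone threshold it does not (step 4).
- **Timing.** A reader might take Protocol 6.2 to mean runs while data accrue. The text does not say so, and its next sentence points to the end of the study. Protocol 6.5 also keeps the outcomes from investigators until closure. What remains is two phrases to reconcile.
- **Sensitivity and status.** Leaving sensitivity to an in vitro study is disclosed, and the SAP calls the study exploratory.

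None of this fixes a version or a threshold. The exploratory label also sits beside a stated H0/H1 and a rule that licenses a claim. SAP 3.2 further expects models from these data to inform algorithm development, so the line between evaluated and developed versions needs to be drawn in writing.

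**Conclusion.** The point holds as a gap in pre-specification. SAP 3.1 can be satisfied by choice of algorithm or cut-off, because neither is fixed before the data are used.

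- **Several different algorithms:** the false-claim chance at true specificity 98% rises from 5.3% to at most 15% for three or 24% for five. These are illustrations that assume the count and independence; positive correlation brings them down towards 5.3%.
- **One tuned threshold:** the 5.3% is kept, assuming one continuous score, one monotone cut-off and independent ears. The pass becomes certain, so the H0/H1 test says nothing about the algorithm, and the lost sensitivity goes unseen here. If several parameters were tuned together, the nesting argument would no longer guarantee the 5.3%.

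The documents do not show that either will happen; they leave both open. This is a cheap improvement that decides whether the specificity claim can be taken at face value.

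**What to change.** 1. In SAP 3.1, name one algorithm version and threshold, archived with a date before any study recording is processed. Make the wording of SAP 2.2 and 3.1 singular, and apply the H0/H1 rule to that version only.
2. Report any other algorithm or retuned threshold as exploratory, with cross-validation across patients.
3. Reconcile the two timing statements in Protocol 6.2, consistent with Protocol 9.1 and SAP 4.
4. Optionally, report beside the specificity the sensitivity of the same archived threshold from the in vitro study.

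**Cost:** wording in both documents and one archived file, with no extra patients. The downside is that later or retuned versions cannot claim the H0/H1 result on these data. The alternative, several algorithms under a Bonferroni rule with zero false positives, would need ln(0.05/K)/ln(0.98) normal insertions, rounded up: 183, 203 or 228 for K = 2, 3 or 5, against 149 for one.
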